## 5.3. Inclusion criteria

1. Histologically confirmed, previously untreated, non-metastatic adenocarcinoma of the prostate using the Gleason scoring or grade group system (histological confirmation can be based on tissue taken at any time, but a re-biopsy should be considered if the biopsy is more than 12 months old).
2. PSA <50ng/ml prior to starting ADT.
- 3.1. NCCN localised high risk or locally advanced disease
  - T3a, T3b or T4 N0M0 (clinical and/or MRI) and/or
  - Grade group 4 or 5 (Gleason 8-10) and/or
  - PSA >20;or
- 3.2. NCCN intermediate risk disease
  - T2b-c N0M0, and/or Grade group 2 or 3 (Gleason 7) and /or PSA 10-20 ng/mland
  - DIL lesion >10mm on staging MRIand
  - One additional adverse feature, for example: Maximum tumour length (MTL) >6mm and/or ≥50% biopsy cores positive and/or >50% involvement measured in mm cancer length /total biopsy length.
4. Age ≥18 years.
5. Signed, written informed consent.
6. WHO performance status 0-2 (Appendix 1).

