## 13. STATISTICAL CONSIDERATIONS

### 13.1. Statistical design and sample size

It is assumed that Failure Free Survival (FFS) at 5 years in the control arm (A) will be 80%. This estimate is based on unpublished data from high risk patients in CHHiP, which showed 5-year biochemical progression free rates of 84.4% [2]. Results from the M0 control cohort of the STAMPEDE trial [64] (a higher risk group than planned for PIVOTALboost), i.e. a FFS of 75% at 5 years in a subgroup of M0 N0 patients with planned RT (n=121) have also been considered.

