#### Initial sample size calculation:

The study was powered to detect a 7% difference in 5-year FFS for each experimental arm compared to A (B, C or D) from 80% to 87%. This difference corresponds to a hazard ratio (HR) of 0.624 for each experimental arm as compared to A. This HR was chosen as sufficient to warrant a change in practice in the knowledge that more extreme effects have been reported in similar settings e.g. HR=0.47 in the ASCENDE trial [65]. In order to adjust for multiplicity [66] the 2-sided significance level for each comparison is set to 0.017 (0.05/3). As it was acknowledged that it could be easier to recruit more patients in the A vs. B comparison (see section 13.2 below), we allowed for more patients in the A vs. B comparison:

- to achieve 85% power to detect a 7% difference in 5 year FFS between A and B, 517 patients per group are needed (502 per group to observe 217 events, plus 3% for loss to follow-up).
- to achieve 80% power to detect a 7% difference in 5 year FFS between A and C (or A vs. D), a total of 918 patients are needed (a total of 892 to observe 193 events, plus 3% for loss to follow-up). The overall sample size for A vs C (A vs D) remains the same when the allocation ratio A:C (A:D) is 2:3 or 1:1.

Treatment allocation will be by minimisation. For the 2 way randomisation (A vs B) the ratio will be 1:1. Treatment allocation in the 4 arm randomisation was based on using a 2:2:3:3 ratio initially as it was expected fewer sites will be able to offer boost treatment groups (C and D). The plan was to closely monitor recruitment and adjust the allocation ratio in the 4 arm randomisation to 1:1:1:1 to ensure 9:9:8:8 (517:517:459:459) final relative numbers. The overall sample size was therefore **1952** patients.

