#### Updated sample size calculation:

Recruitment to the 4 arm randomisation was slower than expected and the switch to 1:1:1:1 was not made. This has meant that the sharing of arm A patients for the B comparisons compared to the C and D comparisons is less than expected (from assumed 90% (459:517) it is around 20% (144 shared A's out of 763) by February 2022). This means that recruitment into A vs C vs D needs to continue beyond arm B completing target recruitment.

The sample size for A vs C and A vs D has been revisited under this scenario, keeping the same sample size assumptions, but allowing for the fact that recruitment would not be complete in 4.5 years. With the recruitment period extended by 2 years to 6.5 years and the pattern of staggered recruitment to date used the following is true:

- to achieve 80% power to detect a HR of 0.624 (translating to a 7% difference in 5 year FFS between A and C (or A vs. D), assuming 5 year event free rate of 80% in arm) and retaining a conservative alpha of 0.017, 192 events are required (under 1:1 allocation). This number of events would be observed if 847 patients, (822 plus 3% for loss to follow-up) are recruited over 6.5 years and followed up for 5 years. The overall sample size for A vs C (A vs D) remains the same when the allocation ratio A:C (A:D) is 2:3 or 1:1.

Once arm B has completed target recruitment, the trial will recruit patients to arms A, C and D in the ratio 1:1:1. Recruitment will be complete when 847 patients have been randomised to Arms A and C and 847 patients have been randomised to Arms A and D. Overall, the total recruitment across all four arms will be 2195 (see appendix 4, for details based on recruitment up to Feb 2022).

The sample size calculation is based on the log-rank test using the 'artsurv' command in STATA, incorporating 4.5 years of staggered recruitment and a minimum of 5 years of follow-up.

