### **13.2. Treatment Allocation**

During the design of the study, it was acknowledged that recruitment and allocation into the different treatment arms could evolve during the trial, given the number of sites open, and the type of boost available at each site. We ran simulations to explore how this would affect time to complete overall recruitment. Following this, we decided to start the trial using an allocation ratio of 2:2:3:3, so it favours the boost groups C or D in a period where it is expected less sites would be offering the boost treatment groups. The allocation ratio may be adjusted during the trial to ensure 9:9:8:8 final relative numbers. Recruitment will be closely monitored and allocation ratios will be monitored annually. On completing recruitment to AvB comparison, the treatment allocation will be 1:1:1 A:C:D.

Full details on the allocation ratio and simulation study will be provided in the Statistical analysis Plan.

Treatment allocation is by minimisation with a random element; balancing factors will be:

- Randomisation Option 1: centre, NCCN risk group (intermediate, high) and suitable volume for focal boost (yes/no).
- Randomisation Option 2a/2b: centre, NCCN risk group (intermediate, high), suitable boost volume for focal boost (yes/no), type of boost (whole gland HDR, focal HDR or focal IMRT) – the last 2 factors will be combined to obtain excluding categories.

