### **13.6. Analysis plan**

The principal analysis will occur after a median follow-up of five years or the target numbers of events have been reached, whichever occurs first. A total of 820 events (217 events x 2 (A, B) + 193 events x 2 (C, D)) to detect a difference of 7% with 85% (A vs B) or 80% (A vs C, D) power is required. Should the analysis not be event driven, the timing will be subject to approval from the IDMC.

The primary comparisons will compare each of the experimental arms to the standard (i.e. A vs B, A vs C and A vs D) and will include all randomised patients (intention-to-treat analysis). Only contemporaneously randomised controls will be used for the A vs C and A vs D comparisons. As secondary analyses, comparisons between experimental arms will also be reported, as well as the overall impact of prostate IMRT vs prostate and pelvis IMRT (A+C vs B+D) and no prostate boost vs prostate boost (A+B vs C+D). Exploratory analysis of the heterogeneity of treatment effect across whole gland or focal boosts, and type of focal boost (IMRT or HDR) will be performed.

All treatment effects will be presented with 2-sided 95% confidence intervals. Adjustment will be made for multiple testing as appropriate. Time to event endpoints will be summarised presenting estimated Kaplan-Meier curves (by treatment); the time point of primary interest is 5 years from randomisation, which will be presented with 95% CI for each treatment arm. Treatment effects will be estimated and tested for significance by the Cox proportional hazards model, adjusting by stratification factors.

Adjusted models will include the duration of ADT prior to starting radiotherapy (as a result of COVID19 related delays to radiotherapy starting). Further models adjusting by other important known prognostic factors will also be fitted. Methods to account for non-proportionality will be used if appropriate. Acute and late side effects will be summarised as frequencies and percentages at each time point. Acute toxicity will also be summarised as worst toxicity reported during radiotherapy. The proportion experiencing grade $\geq$ 2 side effects will be presented; comparisons between treatment groups will be tested using chi-squared or Fishers exact tests. Logistic regression models will be used to estimate treatment differences (odds ratios). Analysis of QL and health economic endpoints are further detailed in Section 20.

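### The tested FFS model uses only the stratification factors; adding baseline PSA, grade group and T stage would gain power at almost no cost

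*Protocol*

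**What the plan says.** Section 13.6 names the model that carries the test for A vs B, A vs C and A vs D: "Treatment effects will be estimated and tested for significance by the Cox proportional hazards model, adjusting by stratification factors". For the boost randomisation, section 13.2 lists the factors as "centre, NCCN risk group (intermediate, high), suitable boost volume for focal boost (yes/no), type of boost" (the last two combined into one factor). Option 1 uses centre, risk group and boost-volume suitability.

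On other covariates, section 13.6 says: "Further models adjusting by other important known prognostic factors will also be fitted". It does not name them. It also says that adjusted models will include the duration of ADT before radiotherapy. Further method detail is deferred to the SAP.

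Section 5.3 makes the three variables part of entry. One criterion is "PSA <50ng/ml prior to starting ADT", and T stage, grade group and PSA together define the NCCN high and intermediate risk categories.

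On sizing, section 13.1 assumes 80% 5-year FFS in arm A and a rise to 87%: "This difference corresponds to a hazard ratio (HR) of 0.624 for each experimental arm as compared to A". The updated calculation is "to achieve 80% power to detect a HR of 0.624", at two-sided alpha 0.017, with 192 events from 822 men (847 with 3% loss). It uses a log-rank test without covariates.

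**The concern.** Two levels of NCCN group summarise three prognostic variables coarsely. The high-risk level is defined by and/or criteria. It pools a man who qualifies on T3a alone with a man who has T4 disease, grade group 5 and a PSA just under 50 ng/ml. The tested model does not use the information that remains within a level.

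In a Cox model, leaving out a prognostic covariate pulls the treatment hazard ratio towards 1 even when the arms are perfectly balanced. A test that includes the covariate therefore has more power. A vs C and A vs D are sized at 80% power at a strict alpha, so they have little reserve, and the covariates need no extra patients or procedures. Because the further models are unnamed, the choice of covariates is also open until someone fixes it.

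**Working it through.** **1. Reproducing the design (A vs C; A vs D is sized the same way).**
- HR = ln(0.87)/ln(0.80) = 0.624.
- Schoenfeld events: 4 × (2.387 + 0.842)² / (ln 0.624)² = 188.
- Freedman events: (2.387 + 0.842)² × (1.624/0.376)² = 195. The stated 192 lies between the two.
- Power with 192 events: Φ(√(192/4) × 0.4716 − 2.387) = Φ(0.880) = 0.811.
- With exponential hazards, the 13 half-year accrual weights in Appendix 4 and 5 further years of follow-up, event probabilities are 0.281 (A) and 0.186 (C). At 1:1, 822 × (0.281 + 0.186)/2 = 192. Then 822 × 1.03 = 847.

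The plan's figures reproduce.

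**2. Simulation.** Inputs from the protocol: 822 men, 1:1, Appendix 4 accrual, control 5-year FFS 80%, two-sided alpha 0.017. Assumed, because the protocol does not give them: a correlated mix of PSA, grade group (2 to 5) and T stage filtered through the eligibility rules, with 85% high risk; and the covariate hazard ratios in the table. Arms were balanced within NCCN group.

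Model S: arm + NCCN group. Model P: the same plus log PSA, grade group and T stage. There were 2,000 trials per row and reading.

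The design effect was read in two ways. *Conditional*: 0.624 is the HR given the covariates. *Marginal*: the population 5-year FFS goes from 80% to 87%, and the conditional HR is solved to match.

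| Residual SD of log hazard within NCCN group (C-index) | Assumed HR: PSA doubling / GG4 v GG2 / T3b-4 v T2 | Conditional: S → P (gain) | Marginal: S → P (gain) |
|---|---|---|---|
| 0 | 1 / 1 / 1 | 80.4% → 80.2% (−0.2) | 79.8% → 79.7% (−0.1) |
| 0.30 (0.60) | 1.15 / 1.6 / 1.37 | 79.6% → 80.2% (+0.6) | 81.0% → 81.3% (+0.3) |
| 0.47 (0.66) | 1.3 / 2.0 / 1.76 | 75.2% → 79.1% (+3.9) | 79.1% → 82.2% (+3.0) |
| 0.63 (0.70) | 1.4 / 2.5 / 2.30 | 71.7% → 79.2% (+7.5) | 77.9% → 84.5% (+6.5) |
| 0.86 (0.76) | 1.6 / 3.5 / 3.00 | 65.4% → 79.1% (+13.7) | 76.4% → 89.9% (+13.6) |

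Gains were taken before rounding. Monte Carlo error is about √(0.8 × 0.2/2000) = 0.9 points per power figure. The attenuation is visible: at SD 0.63 on the conditional reading, the mean fitted HR is 0.643 in model S and 0.620 in model P.

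**3. Type I error.** At HR 1 and SD 0.63 (3,000 trials) both models reject in 0.015 of trials. The Monte Carlo error is √(0.017 × 0.983/3000) = 0.002, so this agrees with 0.017.

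**4. Two side checks, each with a single continuous prognostic score instead of the three covariates.**
- Unequal split. Appendix 4 implies 144 + 246 = 390 in A and 212 + 246 = 458 in C, which scales to 378:444 of 822. On the conditional reading, at SDs of 0.4, 0.6 and 0.8, power goes from 76.8% to 79.6%, 74.4% to 78.5% and 69.7% to 78.4%. The split does not change the picture.
- A vs B, with uniform 4.5-year accrual assumed: gains of about 2, 5 and 7 points at the same SDs.

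**The case against.** The strongest objection concerns the meaning of 0.624. Section 13.1 derives it from a population contrast, 80% to 87%, and sizes the trial with a log-rank test without covariates. That is a marginal effect. On that reading the stated model keeps 76% to 81% power across the table, and 78% to 79% at moderate prognostic strength. A reader might infer from the conditional column that the stated test falls well short of its target. The documents do not support that. The shortfall is real only if 0.624 is taken as the conditional HR, and otherwise the points are a gain not taken. This part of the objection stands.

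It also stands that NCCN group is built from PSA, grade and T stage, so only the residual information is unused. The wide ranges are in the high-risk level; intermediate risk is bounded at T2b-c, Gleason 7 and PSA 10-20. The tested model also carries centre and boost factors, which the simulation left out.

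The size of the gain cannot be read from the protocol. If the residual SD is 0.30, the gain is under 1 point.

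Adjusting for the allocation factors is an accepted primary analysis, and naming covariates is often SAP content. That does not dispose of the point, because section 13.6 itself chooses the tested model and assigns other prognostic factors to different models. Nor is there a problem of competing results: 13.6 designates one test and the others support it.

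**Conclusion.** The point holds as an efficiency improvement. At assumed residual SDs of 0.47 to 0.63 within NCCN group, adding the three covariates raises A vs C power by about 3 to 7.5 points, on either reading of the design effect. Over SDs of 0.3 to 0.86 the range is about 0 to 14. The downside is at most about 0.2 points if the covariates carry nothing, with type I error unchanged. The same sizing makes the result relevant to A vs D. For A vs B the support is lighter, since only a continuous score was tried and 85% starting power leaves less room.

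A reader might go further and infer that the primary test is invalid or the trial underpowered. Neither follows: type I error is held, the stated event and patient numbers reproduce, and planned power is roughly met on the marginal reading. The gain depends on case mix and covariate hazard ratios that were assumed. The SAP, which is not at hand, may already name the covariates; if so, section 13.6 should be aligned with it.

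**What to change.** In section 13.6, state that the tested Cox model for the primary comparisons adjusts for the stratification factors plus pre-ADT PSA (log scale), grade group and T stage. The trial team should choose the categories and say whether clinical or MRI T stage is used, since section 5.3 allows either. Report the stratification-factor-only model as a sensitivity analysis.

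Fix this before any unblinded efficacy analysis. Section 13.7 has the IDMC seeing efficacy data at least yearly, so the choice should be made by people without access to FFS results by arm.

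The cost is a sentence or two in 13.6 with a matching SAP entry, and no extra patients or assessments. In the coding used above the model gains six parameters against about 190 events. The team should confirm that the eCRF holds the actual PSA, grade group and T stage, and not only the risk group. The HR becomes conditional on more covariates, but it is already conditional on the stratification factors, and the planned Kaplan-Meier 5-year estimates are unaffected.

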## **7. RANDOMISATION**

Patients must be randomised centrally by the trials unit (ICR-CTSU) before trial treatment can commence.

Patients should be randomised by telephoning ICR-CTSU on **[name]**

or emailing [[contact]](mailto:[contact]) to request a call back\*

09.00-17.00 (UK time) Monday to Friday

\*During the COVID-19 pandemic, in periods when the ICR-CTSU are working remotely, randomisations may be managed via email, [[contact]](mailto:[contact]). Please refer to the most recent guidance provided by the trials team.

**Randomisation should take place as close to the start of radiotherapy treatment as possible.** An eligibility and randomisation checklist must be completed prior to randomisation.

The following information will be required at randomisation:

- Name of hospital, consultant and person randomising patient
- Confirmation that patient has given written informed consent for trial and for any sub-studies;
- Confirmation that patient is eligible for the trial by completion of the eligibility checklist
- Patient's full name, hospital number, date of birth, postcode and NHS/CHI number
- Randomisation option (2 arms or 4 arms), NCCN risk group (intermediate or high), boost volume identified at staging MRI (suitable for a focal boost or not) and, in case of the 4-arm randomisation, type of boost (whole gland HDR or focal HDR or focal IMRT).

The caller will be given the patient's unique randomisation number (Trial ID) and treatment allocation (see section 14.2).

ICR-CTSU will send written confirmation of trial entry to the data management contact at the recruiting centre.

PIVOTALboost arm B closed to recruitment in Q2 2022

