## **10.2. Treatment timelines**

Radiotherapy treatment should commence ideally within 8 weeks following randomisation and within 6 months of starting hormone therapy (see 10.3). Delays to radiotherapy (with extended ADT) due to COVID19 clinical management strategies are permitted and should be documented (details of how to do this are given in the Trial Guidance notes).

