## **10.5. Radiotherapy planning and delivery**

All participants will be planned to receive 15 or 20 fractions of radiotherapy delivered daily. External beam radiotherapy planning will ideally be performed during month 2-4 (maximum 6) of ADT and radiotherapy treatment will commence within 6 months of ADT. Delays to radiotherapy (with extended ADT) due to COVID19 clinical management strategies are permitted and should be documented (details of how to do this are given in the Trial Guidance Notes).

If participants are allocated to a HDR implant, the HDR implant will be scheduled 14-21 days before starting EBRT (EBRT will consist of 15 fractions for arm C1 or C2 and 20 fractions for arm D1 or D2). EBRT planning will be carried out before or after the HDR implant. EBRT is started two to three weeks after the HDR (day 0). However, if it is standard protocol in the unit, HDR implant can be scheduled 2-3 weeks after completion of EBRT subject to RTQA approval. The first acute toxicity assessment occurs during week 1 of EBRT.

Radiotherapy planning and outlining should be carried out in accordance with the guidelines in the current version of the radiotherapy planning and delivery guidelines, available in the PIVOTALboost site investigator file and on request from ICR-CTSU ([contact]).

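### The ADT-duration covariate in section 13.6 runs to the start of radiotherapy, so part of it accrues after randomisation and can distort the ADT-adjusted treatment effect

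*Protocol*

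**What the plan says.** Section 13.6 first sets out the model for the treatment effect: "Treatment effects will be estimated and tested for significance by the Cox proportional hazards model, adjusting by stratification factors". The primary comparisons "will include all randomised patients (intention-to-treat analysis"). It then adds: "Adjusted models will include the duration of ADT prior to starting radiotherapy (as a result of COVID19 related delays to radiotherapy starting"). The section does not say whether this ADT-adjusted model is primary or supportive.

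The timing is set elsewhere in the protocol:

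- Section 7: "Patients must be randomised centrally by the trials unit (ICR-CTSU) before trial treatment can commence", and "Randomisation should take place as close to the start of radiotherapy treatment as possible".
- Section 10.2: "Radiotherapy treatment should commence ideally within 8 weeks following randomisation", with COVID-related delays permitted.
- Section 10.5, for patients allocated to HDR: "the HDR implant will be scheduled 14-21 days before starting EBRT". The same section allows the implant 2-3 weeks after EBRT where that is the unit's standard and quality assurance agrees.
- Section 13.3: failure-free survival is timed from randomisation.
- Section 13.2: the balancing factors for options 2a and 2b are "centre, NCCN risk group (intermediate, high), suitable boost volume for focal boost (yes/no), type of boost". ADT duration is not among them.

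**The concern.** A covariate in a model of a randomised comparison should be fixed before allocation. This one is a sum of two intervals: ADT start to randomisation, which is baseline, and randomisation to radiotherapy, which is not. If the second interval differs by arm, the model conditions on a consequence of treatment allocation. It can then remove part of a real effect, because the extra ADT weeks came with the allocated treatment. It can also create a spurious one, because delay shares causes with failure.

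The model is there because of pandemic delays. An adjustment that adds an arm-related distortion of its own would be hard to interpret beside the stratification-adjusted result, particularly for A vs C and A vs D.

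**Working it through.** **1. The design effect.** With 5-year FFS of 80% and 87% (section 13.1), HR = ln(0.87)/ln(0.80) = 0.6241. This reproduces the stated 0.624, which is used below as the reference. The protocol gives no figure from which a bias could be computed, so everything after step 3 rests on stated assumptions.

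**2. Which part of the covariate is post-randomisation.**

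| Interval | Protocol limit | Status |
|---|---|---|
| ADT start to randomisation | up to 6 months (5.4); no limit if COVID-affected (10.3) | baseline |
| Randomisation to radiotherapy | ideally within 8 weeks (10.2); longer delays permitted | after allocation |
| Whole covariate | 6 months; under 12 months if COVID-affected (10.2, 10.3) | mixed |

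**3. Where it could depend on arm.** Arm A has no implant. In HDR patients of C and D, the implant may come 14-21 days before EBRT. If the start means the first EBRT fraction and HDR is given first, their interval can be longer. The protocol is not uniform on this origin: sections 8.4.1 and 8.4.2 count from the first external beam fraction, section 8.4.3 from the first radiotherapy fraction, and section 12.2 includes the implant in the commencement of study treatment. Intended boost type is fixed before randomisation, so adjusting for it does not remove a difference between arms within the HDR stratum.

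**4. Extra ADT weeks affect failure (assumed).** Let g be the hazard ratio per month of ADT and s the arm difference in months. Then adjusted HR = total HR / g^s, with s = 14/30.4 = 0.46 or 21/30.4 = 0.69.

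| g (assumed) | s = 0.46 | s = 0.69 |
|---|---|---|
| 1.00 | 0.624 | 0.624 |
| 0.95 | 0.624/0.95^0.46 = 0.639 | 0.624/0.95^0.69 = 0.647 |
| 0.90 | 0.624/0.90^0.46 = 0.655 | 0.624/0.90^0.69 = 0.671 |

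These figures apply the shift to the whole arm. If half the arm were HDR-first (also assumed), the average shift halves to 0.23-0.35 month, and at g = 0.90 the result is about 0.639-0.647.

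**5. A common cause of delay and failure (assumed).** Cox models were fitted to simulated trials of 400,000 patients per scenario. The data-generating HR was 0.624, mean ADT before randomisation about 3 months, and mean randomisation-to-radiotherapy interval about 1.5 months in arm A. One standard deviation of an unmeasured factor added 0.5 month of delay and 0.3 to the log hazard. ADT itself had no effect.

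| Arm shift | Unadjusted | Adjusted, ADT to radiotherapy | Adjusted, ADT to randomisation |
|---|---|---|---|
| none | 0.636 | 0.635 | 0.636 |
| 0.46 month | 0.627 | 0.598 | 0.627 |
| 0.69 month | 0.626 | 0.584 | 0.626 |

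The comparison is across each row, on the same simulated patients. At equal delay, patients in the later-starting arm carry less of the adverse factor, so the HR falls. A factor that delayed treatment but lowered the hazard would push it the other way.

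**6. Both mechanisms together.** At 0.46 month the HR moved from 0.615 to 0.602 (g = 0.95) and from 0.594 to 0.595 (g = 0.90). The two can partly cancel.

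**7. The alternative covariate.** In every scenario run, adjusting for ADT duration up to randomisation left the HR within 0.001 of the unadjusted value. With no arm shift, adjusting to radiotherapy start also changed it by at most 0.001.

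**8. Missing values.** A patient who never starts radiotherapy has no value for this covariate. A complete-case fit would drop that patient, although the comparison is meant to keep everyone randomised.

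**The case against.** A reader might infer that the trial's treatment effect is biased, or that C and D differ from A by 2-3 weeks by construction. The documents support neither.

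- The sentence just before the disputed one already estimates and tests the effect in a model adjusted for stratification factors. The natural reading is that the ADT model is supportive. This stands, although the protocol does not say so.
- All arms share the same windows: ideally 8 weeks from randomisation and within 6 months of starting ADT. An implant 14-21 days before EBRT fits inside 8 weeks and may not delay EBRT at all.
- C and D mix whole-gland HDR, focal HDR and focal IMRT, and no HDR share is given. A shift needs an HDR patient, HDR given first, EBRT counted as the start, and no earlier booking of the implant. Section 20.1 lists extra preparation for HDR and focal IMRT, but nothing in the protocol states a delay for either, or for pelvic fields.
- Section 10.3 sets ADT by total duration, so a few more weeks before radiotherapy need not change total exposure, and g could be 1.
- Loss of non-starters presumes complete-case handling, which the protocol does not state. Section 13.6 also defers the handling of COVID-affected data to the SAP.

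These points limit the size and reach of the problem. They do not make the covariate a baseline one, and the protocol text itself fixes it.

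**Conclusion.** The point holds as a conditional one. Section 13.6 commits the adjusted models to a covariate that is partly post-randomisation and that may differ by arm for HDR patients in C and D. Distortion needs an arm difference in time to radiotherapy, and in addition either an effect of the extra weeks on failure or a common cause of delay and failure.

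Under an assumed 2-3 week shift across a whole arm, 0.624 moves to 0.639-0.671 for an assumed 5-10% lower hazard per month. Under the assumed common cause it falls by 0.627 - 0.598 = 0.029 to 0.626 - 0.584 = 0.042. With no arm difference, or with neither mechanism, there is essentially no change. The whole-arm figures overstate the shift if only some patients have HDR first, so none of them is an estimate for this trial.

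The stratification-adjusted Cox model is not shown to be affected. The change is still worth making, because a baseline version of the covariate is available.

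**What to change.** In section 13.6:

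1. Replace the covariate with duration of ADT at randomisation (date of ADT start to date of randomisation), optionally with calendar period relative to the pandemic.
2. State that the stratification-adjusted Cox model in all randomised patients is the primary analysis.
3. Report the randomisation-to-radiotherapy interval descriptively by arm, preferably also by intended boost type.
4. If a model using ADT to radiotherapy start is kept, label it a sensitivity analysis only. Define the start as implant or first EBRT fraction for HDR patients, and say how patients who never start are handled.

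The cost is small. Both dates are already needed to apply the exclusion on prior ADT at randomisation (section 5.4), so no new data are collected. The one loss is that COVID delay arising after randomisation is no longer adjusted for. That should be the smaller part, since section 7 asks for randomisation close to radiotherapy and section 10.3 lets the extended ADT of affected patients fall before randomisation.

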Further details of analysis methods will be specified in a Statistical Analysis Plan in accordance with ICR-CTSU Standard Operating Procedures. The Statistical Analysis Plan will include a section to detail how data impacted by strategies introduced to mitigate risks relating to the COVID19 pandemic will be handled.

Any quality of life data collected from PIVOTALboost participants within the SPRUCE study will be shared with PIVOTALboost for analysis.

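### Section 13.6 gives clinician-graded late toxicity no summary that allows for unequal follow-up; a 5-year cumulative incidence could be added cheaply from data already collected

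*Protocol*

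**What the plan says.** Section 8.4.3 schedules late toxicity (CTCAE and RTOG) at seven visits: 6, 12, 18, 24, 36, 48 and 60 months from the first radiotherapy fraction. Section 13.4 names these scales for late toxicity but gives no threshold, window or time-to-event form.

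Section 13.6 sets the analysis:
- The general rule for both phases is "Acute and late side effects will be summarised as frequencies and percentages at each time point".
- A further summary is then added for one phase only: "Acute toxicity will also be summarised as worst toxicity reported during radiotherapy". There is no matching sentence for late toxicity.
- For the proportion with grade 2 or worse, "comparisons between treatment groups will be tested using chi-squared or Fishers exact tests", with odds ratios from logistic regression. It does not say whether the late proportion is per visit, at 5 years or at any time.
- On multiplicity, "Adjustment will be made for multiple testing as appropriate".

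On timing, section 13.6 says "The principal analysis will occur after a median follow-up of five years", or once the target events are reached if that comes first. The sample size in section 13.1 was calculated "incorporating 4.5 years of staggered recruitment and a minimum of 5 years of follow-up". Section 13.6 also says "Further details of analysis methods will be specified in a Statistical Analysis Plan".

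**The concern.** The primary objective (section 2.1) pairs better failure-free survival with similar bladder and bowel side effects. A reader will therefore want to know, for each arm, what share of men had a grade 2+ late effect within five years. The stated methods do not give that figure cleanly. Visit percentages show burden and recovery, but they count only men affected around that visit, so when effects resolve they fall well below the share ever affected. A crude ever-affected proportion counts a man followed for three years as if he had been followed for five. The background in section 1.1.8 itself quotes cumulative grade 2+ rates at 12 and 36 months from the pilot studies, so as written section 13.6 yields no figure comparable with those.

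**Working it through.** There is no stated figure to reproduce, because the protocol gives no power or expected rate for late toxicity. The check asks how the stated methods behave under the trial's own accrual. **All toxicity rates and durations are assumed.**

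**1. Accrual (Appendix 4).** Arm A: 144 + 246 = 390. Arm C: 212 + 246 = 458. The first 144 and 212 enter over the eight half-years to the end of 2021; the remaining 246 per arm are spread evenly over months 50 to 78. Median entry is about month 54, so a median of five years falls at month 54 + 60 = 114. A minimum of five years falls at month 78 + 60 = 138.

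**2. Who has 60-month data at month 114?** Men who entered by month 54. Of the later 246, the share is (54 − 50)/28 = 0.143, or about 35 men.
- A: (144 + 35)/390 = 46%
- C: (212 + 35)/458 = 54%
- Together: 426/848 = 50%

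The recruitment fractions in the Appendix 4 Stata code also give 50% at 60 months, with 74% at 48 months and 99% at 36 months.

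**3. Per-visit tests.** Assume 5-year risks of 12% (A) and 20% (C), exponential onset, one episode per man, and the worst grade since the previous visit recorded, as Appendix A3 asks. In simulation, the highest of the seven visit percentages and the best single-visit power at month 114 are:

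| Mean episode | A vs C, highest visit | Best-visit power |
|---|---|---|
| 6 months | 3.6% vs 6.0% | 0.38 |
| 12 months | 4.6% vs 7.7% | 0.50 |
| 24 months | 6.4% vs 10.6% | 0.57 |
| 60 months | 8.9% vs 14.8% | 0.63 |
| Permanent | 12% vs 20% | 0.70 |

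Two repeat simulations gave ranges of 0.35–0.70 and 0.36–0.72.

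Hand checks use power = Φ(|p₂ − p₁|/SE − 1.96), with SE = √[p₁(1−p₁)/n₁ + p₂(1−p₂)/n₂]:
- 6-month episodes, all men: 0.024/0.0146 = 1.65, power 0.38.
- Permanent effects at 48 months: risks 1 − 0.88^0.8 = 9.7% and 1 − 0.80^0.8 = 16.3%, in 285 and 353 men; 0.0663/0.0264 = 2.51, power 0.71.

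**4. Time to first event.** Simulated power at month 114 is 0.82–0.85. Hand check: hazard ratio = ln 0.88/ln 0.80 = 0.573. Using the crude proportions in step 5, events ≈ 0.101 × 390 + 0.174 × 458 = 119. Then z = 0.557 × √(119 × 0.46 × 0.54) = 3.03, power 0.86.

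**5. Crude ever-affected proportion.** At month 114 it reads about 10.1% and 17.4%, with power 0.85–0.88. The relative shortfall is (12 − 10.1)/12 = 16% in A and (20 − 17.4)/20 = 13% in C. A simpler continuous-time calculation, with true risks from 5% to 25%, gives 9–10%.

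**6. Complete five-year follow-up (month 138).** The crude proportion is unbiased. The best visit has power 0.34–0.89 and time to first event 0.89–0.90. Nothing is lost per visit if effects are permanent: 0.08/0.0249 = 3.21, power 0.90.

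**The case against.** The strongest reply is that this is detail for the statistical analysis plan. Section 13.6 defers further methods to it, and nothing there excludes a cumulative measure. That stands as a limit: the point concerns only the method the protocol states, and the plan may already go further. It does not remove the point, because section 13.6 fixes a summary, tests and an effect measure for late toxicity, and none of them uses time.

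Second, the tested grade 2+ proportion can be read just as naturally as ever affected. That also stands. On that reading power is kept, both arms read low together, and only the 5-year level suffers.

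Three stronger readings are tempting, and the documents do not support them:
- *Seven visits mean an inflated false-positive rate.* Seven unadjusted tests would give at least one p<0.05 in 18–27% of null trials. But section 13.6 promises adjustment for multiple testing where appropriate, so unadjusted testing is not the stated plan.
- *The pooled A+B against C+D comparison is biased.* Follow-up would differ between the pooled groups because option 1 closed earlier, but section 13.6 does not say that late toxicity will be compared there.
- *A cumulative estimate would settle whether side effects are similar.* It would not, because no margin is set.

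Finally, visit prevalence and cumulative incidence answer different questions, and first-event analysis counts a brief episode like a lasting one. That is a reason to report both. Patient-reported effects have their own analysis in section 20.2 and are outside this point.

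**Conclusion.** The point holds as a cheap improvement, not as an error. As stated, section 13.6 has no late-toxicity summary that allows for unequal follow-up, and its own median-five-year trigger would leave about half of the A and C men without 60-month data. In that case per-visit tests usually have less power than a cumulative comparison when effects resolve (about 0.36–0.72 against about 0.84), and a crude ever-affected figure understates 5-year risk by roughly 10–15% in relative terms.

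The power figures rest on assumed risks of 12% and 20%, one episode per man, and assumed onset and duration. With 7% and 14% the pattern is the same: single visits 0.14–0.74 against 0.86–0.88. With complete five-year follow-up the crude bias disappears; with permanent effects as well, so does the per-visit power loss. The primary analysis, sample size and alpha are unaffected.

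**What to change.** Add to section 13.6:

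- Time to first RTOG grade 2+ late event from the 6-month visit, for bladder and bowel separately, as the two key late-toxicity summaries. CTCAE and grade 3+ are supportive. Without this ranking, two domains, two scales and two thresholds would give eight estimates per arm.
- Onset taken as the first positive visit. Report 5-year cumulative incidence by arm, with death as a competing event and loss to follow-up censored, the 5-year difference with 95% CI, and a cause-specific hazard ratio.
- Men already grade 2+ on that scale at baseline left out of the first-event analysis, with a sensitivity analysis that includes them and adjusts for baseline grade.
- Contemporaneous controls for any A vs C or A vs D toxicity comparison.
- Visit percentages kept, to show persistence and recovery, and a statement of whether the tested grade 2+ proportion is per visit or ever affected.

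The cost is some extra analysis and no new data: the seven late assessments and the baseline scores (section 8.1) are already collected. Baseline handling matters: if 5% or 10% of men were grade 2+ at baseline and still so at 6 months (assumed), power would fall from 0.83 to 0.70 or 0.56 with them counted as events, against 0.82 or 0.80 with them left out. The remaining downside is that a brief episode counts the same as a lasting one.
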